#### 7.2.3.2 *Minimal Residual Disease*

MRD status for subjects with a response of CR or CRi will be determined using flow cytometry from a central lab. MRD will be classified as positive or negative. The estimated rates of subjects with negative MRD in subjects with a response of CR or CRi will be provided for each treatment arm given there are sufficient amount of data.

#### 7.2.3.3 *Time To Response (TTR)*

TTR will be presented for each treatment arm based on all randomized subjects with a documentation of response (i.e., CR, CRi, PR, or PRwL). Summary statistics and a 2-sided confidence interval for median TTR will be provided by treatment arm. No treatment comparison will be performed.

### 7.3 **Safety Analyses**

All safety analyses will be performed using the AT analysis set.

#### 7.3.1 **Adverse Events**

Adverse events will be coded using MedDRA Version 16.1 or higher. The Grade of the AE will be assessed according to the NCI-CTCAE Version 4.03. If an AE is not included in the NCI-CTCAE Version 4.03, the Grade of the AE will be assessed according to the protocol, Section **8.2.1.2**.

The summary of AEs will be focused on treatment-emergent AEs. A treatment-emergent AE (TEAE) is defined as any AE that emerges or worsens in the period from the first dose of study treatment to 30 days after the last dose of study treatment. The onset date of an AE will be compared to the first dose date and the last dose date plus 30 days to determine whether the AE is treatment-emergent or not. If the onset date of an AE is completely or partially missing, refer to [Section 6.2.1](#) for the algorithm to determine whether an AE is treatment emergent.

TEAEs will be summarized for each treatment arm by MedDRA system organ class (SOC) and preferred term (PT), or PT only. For summary tables by SOC and PT, SOC will be sorted alphabetically and PT will be sorted by decreasing frequency in the duvelisib arm within each SOC. For summary tables by PT only, PT will be sorted by decreasing frequency in the duvelisib arm.

If multiple TEAEs of the same PT occur within a subject, only the maximum grade observed for this PT will be used in summary of TEAEs by grade, the subject will be counted only once in the number of subjects for this PT and only once for the number of subjects for the SOC to which this PT belongs.

An overview TEAE summary table will be provided, which will include the number of subjects with AEs in selected categories. In addition, TEAEs will be summarized for the following categories, and will be tabulated by SOC and PT, unless otherwise specified.

- Treatment-emergent AEs (All Causalities)
- Treatment-emergent AEs (Treatment-Related)
- Treatment-emergent AEs (All Causalities, by maximum grade)
- Treatment-emergent AEs (Treatment-Related, by maximum grade)
- Grade 3 or higher treatment-emergent AEs (All Causalities)
- Grade 3 or higher treatment-emergent AEs (Treatment-Related)
- Treatment-emergent SAE (All Causalities)
- Treatment-emergent SAE (Treatment-Related)
- Treatment-emergent AEs resulting in discontinuation of study drug (All Causalities)
- Treatment-emergent AEs resulting in dose hold (All Causalities)
- Treatment-emergent AEs resulting in dose reduction (All Causalities)
- Treatment-emergent AEs resulting in dose hold or reduction (All Causalities)
- Treatment-emergent AEs resulting in discontinuation of study drug (Treatment-Related)
- Treatment-emergent AEs resulting in death (All Causalities)
- Treatment-emergent AEs resulting in death (Treatment-Related)
- Treatment-emergent AEs by PT (All Causalities)

- Treatment-emergent AEs by PT (AEs with onset date within 24 weeks after the first dose of study treatment; All Causalities)
- Grade 3 or higher treatment-emergent AEs by PT (All Causalities)
- Grade 3 or higher treatment-emergent AEs by PT (AEs with onset date within 24 weeks after the first dose of study treatment; All Causalities)
- Treatment-emergent SAEs by PT (All Causalities)
- Treatment-emergent SAEs by PT (Treatment-Related)
- Treatment-emergent AEs reported in  $\geq 5\%$  of subjects and occurred at  $\geq 2\%$  higher incidence in subjects receiving duvelisib (All Causalities)
- Grade 3 or higher treatment-emergent AEs reported in  $\geq 5\%$  of subjects and occurred at  $\geq 2\%$  higher incidence in subjects receiving duvelisib (All Causalities)

A by-subject listing of the following AE categories will be presented.

- All AEs (TEAEs will be flagged)
- All SAEs (TEAEs will be flagged)
- Treatment-emergent AEs resulting in dose hold
- Treatment-emergent AEs resulting in dose reduction
- Treatment-emergent AEs resulting in discontinuation of study drug
- Treatment-emergent AEs resulting in death

Treatment-emergent AEs (All Causalities) and Treatment-emergent AEs (Treatment-Related) will also be tabulated in each subgroup specified in [Section 6.5](#).

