- g. Additional scans may be performed (eg, head/neck CT) if clinically indicated or if the area is a site of known disease. Magnetic resonance imaging (MRI) may be substituted if clinically indicated, but the modality chosen to evaluate each individual subject should be the same throughout the duration of the study.
- h. Bone marrow biopsy and/or aspirate are required at Screening as a baseline for response assessment (unless clinically contraindicated). Sample and corresponding pathology report should be sent for biomarker analysis if available.
- i. For all subjects AEs should be monitored from time of the signing of the ICF. Any new medical or worsening preexisting conditions arising after signing the ICF will be captured as an AE for randomized subjects. SAEs for all subjects will be reported from the signing of the ICF as defined in [Section 8.1.3](#).
- j. Dosing should occur within 1 week of randomization after all screening assessments have been obtained and eligibility confirmed.

Table 2: Schedule of Assessments for Subjects Receiving Duvelisib ^a

	Cycle 1 (21±2 days) ^o		Cycle 2 (28±4 days) ^o		Cycles 3 – 7 (28±4 days) ^o	Cycle 9-19 every odd cycle (28±4 days) ^o	> Cycle 19 every odd cycle (28±4 days) ^p	Early Treatment Termination (ETT) from Duvelisib ^q	Safety Follow-up
	D1	D8±2	D1±2	D15±2	D1±4	D1±4	D1±4	≤7 d from last dose	30+7 d from last dose
Concomitant medications & Procedures	X	X	X	X	X	X	X	X	X
AE/SAE assessment ^b	X	X	X	X	X	X	X	X	X
Focused physical examination	X		X		X	X	X	X	
Blood chemistry ^c	X ^d	X	X	X	X	X	X	X	
Hematology ^c	X ^d	X	X	X	X	X	X	X	
Coagulation tests ^c	X ^d								
Serum Immunoglobulins	X				X ^e	X ^e		X ^e	
βhCG pregnancy test ^{c, f}					X	X	X	X	
Blood for Cytogenetics/FISH analysis ^g	X ^{h, i}								
Blood for IGHV mutation analysis ^g	X ^h								
Blood for Immunophenotyping ^{g, j}	X ^k				X ^e	X ^e		X ^e	
Serum for biomarkers ^{g, j}	X ^k		X		X ^e	X ^e		X ^e	
Blood for biomarkers ^g	X ^k		X		X ^e	X ^e		X ^e	
Pharmacogenomics ^g	X ^l								
EQ-5D & FACIT-F	X ^d				X ^m	X ^m	X ^m	X ^m	
ECOG Performance status	X ^d	See Table 5: Disease Response Assessments							

Response assessments		See Table 5: Disease Response Assessments	
Archival tumor tissue	X ⁿ		
Study drug administration	X	Continuous Dosing	

- a. See [Section 6.2](#) and [6.3](#) for additional information on each assessment.
- b. AEs are collected (and SAEs reported) through 30 days post last dose of duvelisib.

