- **Skin rash:** Subjects who develop Grade 3 or higher skin rashes should have duvelisib held until resolution of symptoms. In the setting of new Grade 1-2 skin rash early intervention is recommended to ameliorate risk of worsening symptoms. Evaluation of concomitant medications, environmental exposure, infections or other contributing factors is recommended.
- **Cardiac:** Subjects who develop Grade 3 or higher cardiac events should have duvelisib held until resolution of symptoms. This includes \geq Grade 3 (≥ 500 ms) QT interval corrected with Fridericia's method (QTcF) prolongation. A \geq Grade 3 QTcF prolongation requires triplicate ECGs with the average measurement used and the use of Fridericia's correction method (QTcF). For subjects with a right or left BBB, a Grade 3 QTc prolongation is defined as an increase in QTcF of >100 ms from the pre-dose ECG to any post dose ECG as the QRS interval is prolonged at Baseline (by approximately 40 ms) in subjects with a BBB

Subjects requiring treatment interruption should be re-evaluated at least weekly until the toxicity improves to \leq Grade 1 or returns to Baseline level. Duvelisib dose will be restarted at doses described in [Table 9](#).

Treatment Interruption for Hematologic Toxicity

Worsening or transient Grade 3 or higher neutropenia, anemia, and/or thrombocytopenia caused by the subject's existing disease (CLL or SLL) or by duvelisib are to be expected. Blood counts should be monitored as prescribed in the protocol with the frequency increased as clinically indicated in the setting of new or worsening Grade 3 or higher cytopenias. Duvelisib dosing may be interrupted at any time, at the discretion of the treating physician.

Treatment with duvelisib should be interrupted for the following symptomatic hematologic toxicities:

- Grade 3 or higher febrile neutropenia
- Grade 3 or higher thrombocytopenia associated with Grade 2 or higher haemorrhage

The subject should be re-evaluated at least weekly until the toxicity improves to \leq Grade 1 or returns to Baseline.

Duvelisib may be withheld up to 42 days for toxicity. Doses withheld for > 42 days due to treatment-related toxicity will result in permanent discontinuation from treatment. Any subject who requires a dose < 5 mg BID due to treatment-related toxicities will be permanently discontinued from treatment. Dose levels are shown in [Table 9](#).

Table 9: Dosing Levels Duvelisib

Dose Level	Dose (mg)
1	25 BID
-1	15 BID
-2	10 BID
-3	5 BID

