6.3.4 Adverse Events

For all subjects (including screen-failures), monitoring of AEs will be performed from the signing of the ICF. For randomized subjects, AEs will be collected on the AE eCRF from the signing of the ICF through 30 days after the final dose of either duvelisib or ofatumumab.

See [Section 8.2](#) for a full description of the collection and reporting of AEs during this study.

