6.5 POST-TREATMENT PERIOD

6.5.1 Safety Follow-up Visit (30 Days Post-Treatment)

6.5.1.1 *Duvelisib*

For subjects randomized to duvelisib, a visit should occur 30+7 days after discontinuation or last dose of duvelisib as outlined in [Table 2](#). If possible, this visit should be conducted prior to initiation of any subsequent therapy. This visit may be a conducted as a phone screen as long as the study subject does not require laboratory and/or other assessments related to any new or ongoing AEs, in which case a clinical visit will be required. Assessments should include:

- AEs/SAEs collection
- Concomitant medications and procedures collection

Following the last dose of duvelisib, subjects will continue follow-up as described in [Table 2](#) and [Table 5](#).

6.5.1.2 *Ofatumumab*

For subjects randomized to ofatumumab, a visit should occur 30+7 days after discontinuation or last administration of ofatumumab. If possible, this visit should be conducted prior to initiation of any subsequent therapy. This visit may be a conducted as a phone screen as long as the study subject does not require laboratory and/or other assessments related to any new or ongoing AEs, in which case a clinical visit will be required. Assessments include:

- AEs/SAEs collection
- Concomitant medications

Following the last dose of ofatumumab, subjects will continue follow-up as described in [Table 4](#) and [Table 5](#).

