8.2.2.3 Persistent or Recurrent Adverse Events

A persistent AE is one that extends continuously, without resolution, between subject evaluation time points. Such events should only be recorded once on the AE eCRF (and SAE Report Form, if applicable). If a persistent AE changes in grade, it should be recorded as a new AE on the eCRF.

A recurrent AE is one that occurs and resolves between subject evaluation time points, and subsequently recurs. All recurrent AEs should be recorded on the eCRF (and SAE Report Form if applicable).

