### 7.3.2 Laboratory Data

Laboratory tests will be reported separately for hematology and blood chemistry.

For the purposes of presentation in both tables and listings, the following laboratory test results will be converted to the International System of Units (SI) before presentation: sodium, potassium, chloride, bicarbonate (or CO2), albumin, total protein, creatinine, uric acid, calcium, phosphorus, magnesium, glucose, total and direct bilirubin, and alkaline phosphatase, red blood cell (RBC) count, hemoglobin, hematocrit, platelets, white blood cell count with 5-part differential performed manually or by flow cytometry (lymphocytes, neutrophils, monocytes, basophils, and eosinophils), etc.

Lab tests performed after the start of the first dose of study treatment, up to 30 days from the last dose, will be considered treatment-emergent. Only treatment-emergent lab tests will be included in the analyses in this section.

If a laboratory test value is reported using a non-numeric qualifier (e.g., less than [ $<$ ] a certain value, or greater than [ $>$ ] a certain value), the given numeric value will be used in the summary statistics, ignoring the non-numeric qualifier.

For laboratory tests with NCI-CTCAE grades, a shift table from baseline grade to the maximum post-baseline grade will be provided. Laboratory tests with bi-directional grades (e.g., Hyperglycemia and Hypoglycemia) will be presented separately for each direction within the shift table.

Listings will be provided for all laboratory test results and for laboratory test results grade 3 and higher. A listing of subjects with ALT or AST  $>3xULN$  with simultaneous total bilirubin  $>2xULN$  will be presented, where ULN stands for upper limit of normal. The elevations of ALT/AST and total bilirubin must occur within 2 days of each other.

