### **7.3.6 Deaths**

On-treatment deaths are defined as deaths that occur within 30 days of the last dose of study medication. Deaths on treatment and causes for deaths occurring on-treatment, and deaths during follow-up will be summarized.

A by-subject listing of deaths on study will be presented.

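### When a toxicity hold becomes permanent, adverse events and labs arising after day 30 from last dose but before the decision to stop are left out of the treatment-emergent outputs

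*SAP*

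**What the plan says.** Four rules close 30 days after the last dose.

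- **Treatment-emergent AEs (SAP V4.0, 7.3.1):** an event qualifies only if it "emerges or worsens in the period from the first dose of study treatment to 30 days after the last dose of study treatment". Classification compares the onset date with the last dose date plus 30 days.
- **Labs (SAP V4.0, 7.3.2):** tests after first dose and "up to 30 days from the last dose, will be considered treatment-emergent". Only these enter that section's analyses.
- **Deaths (SAP V4.0, 7.3.6):** "On-treatment deaths are defined as deaths that occur within 30 days of the last dose of study medication".
- **AE collection (Protocol 6.3.4):** "AEs will be collected on the AE eCRF from the signing of the ICF through 30 days after the final dose". Protocol 8.2.1 agrees, and so does Table 2 footnote b: "AEs are collected (and SAEs reported) through 30 days post last dose of duvelisib".

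The duvelisib hold rule in Protocol 4.2.1.1 runs longer. The drug may be withheld for toxicity for up to 42 days, with re-evaluation at least weekly, and "Doses withheld for > 42 days due to treatment-related toxicity will result in permanent discontinuation from treatment". Protocol 8.2.2.3 adds a recording rule: "If a persistent AE changes in grade, it should be recorded as a new AE on the eCRF".

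Neither document says what last dose means when a hold turns into a permanent stop. On the plain reading it is the last dose taken before the hold.

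**The concern.** A subject on a toxicity hold is still under study treatment: seen at least weekly, with a restart possible. Whether an event in the sixth week of the hold is treatment-emergent depends on something that happens afterwards, namely whether the subject recovers enough to resume. Inclusion therefore depends on outcome, and the exclusions fall on subjects whose toxicity did not resolve.

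The site cannot apply the collection rule in real time either. On day 35 of a hold nobody knows whether the last dose has already been given.

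Safety is a secondary objective. At stake are late Grade 3 to 5 worsenings and late labs in the subjects with the most persistent toxicity. Hepatic results matter most here, because Grade 3 or higher transaminase elevation is itself a reason to hold.

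**Working it through.** Neither document states a figure for this gap, so there is none to reproduce. The check is day arithmetic, with the last dose before the hold as day 0.

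1. **Inputs.** Treatment-emergent window: 30 days after last dose (SAP 7.3.1, 7.3.2, 7.3.6). Longest permitted duvelisib hold: 42 days (Protocol 4.2.1.1).

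2. **Uncovered hold time** = max(0, decision day − 30).
   - Decision by day 30: 0 days.
   - Decision on day 35: 35 − 30 = 5 days.
   - Decision on day 42: 42 − 30 = 12 days (days 31 to 42), or 12/42 = 29% of a maximal hold.

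3. **Same event, two outcomes.** Take an AE with onset on day 35.
   - Drug restarts on day 40: last dose is day 40 or later, so the window runs to at least day 40 + 30 = 70. The AE is treatment-emergent.
   - Drug never restarts: the window closed on day 30. The AE is not treatment-emergent.

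4. **Data exist in the gap.** Exactly weekly re-evaluation counted from day 0 gives visits on days 5 × 7 = 35 and 6 × 7 = 42, both in the excluded period.

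5. **Worsening.** Suppose a Grade 3 AE begins on drug, causes the hold, and becomes Grade 5 on day 36. Under Protocol 8.2.2.3 the Grade 5 record is a new AE. Its onset is day 36, and 36 > 30, so it is not treatment-emergent. The maximum-grade table then shows Grade 3, and the table of treatment-emergent AEs resulting in death omits the event. This assumes that the ADaM specifications, which are not among the documents, do not link the two records.

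6. **Labs.** SAP 7.3.2 restricts the whole section to treatment-emergent tests. The section contains the grade shift table and the listing of ALT or AST above 3×ULN with bilirubin above 2×ULN. It also promises a listing of all laboratory results, which sits uneasily with the restriction.

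7. **Ofatumumab.** Table 10 withholds until recovery, and Protocol 4.2.2.1 states no maximum hold. A monthly infusion may be given up to 3 weeks late, which on a nominal cycle is 28 + 21 = 49 days after the previous one. A stop decision can therefore come after day 30 in this arm too, with no stated upper limit on the gap.

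8. **Visit anchors.** Table 2 times the early termination (ETT) visit within 7 days of last dose and the safety visit 30 to 37 days from last dose. Protocol 4.3 and 6.4 also allow ETT to be timed from the decision to stop. Protocol 6.5.1.1 says "a visit should occur 30+7 days after discontinuation or last dose of duvelisib". Counted from a day-42 discontinuation, ETT falls by day 42 + 7 = 49 and the safety visit on days 42 + 30 = 72 to 42 + 37 = 79. Scheduled AE assessments can thus fall after the treatment-emergent window has closed.

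**The case against.** The strongest reply is that a fixed 30-day window is objective and identical in both arms, and that little is actually lost. Much of this stands.

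- The toxicity that caused the hold, and anything else with onset by day 30, is treatment-emergent. A reader might infer that events in subjects who never recover are generally lost. They are not: only onset or worsening from day 31 is affected.
- A reader might infer that late deaths vanish from the duvelisib column. SAP 7.3.6 also summarizes deaths during follow-up and lists all deaths on study, so a day-36 death is reclassified. What may be missing is the fatal treatment-emergent AE entry and a summarized cause, since 7.3.6 attaches causes only to on-treatment deaths.
- Late AEs that are collected appear in the all-AE and all-SAE listings, with treatment-emergent ones flagged (SAP 7.3.1). Existing AEs are followed to resolution, return to baseline or stability (Protocol 8.2.1). SAEs that the investigator suspects are related stay reportable after day 30 (Protocol 8.2.3.1). None of this puts the event in the summary tables, and an unrelated or non-serious event after day 30 has no such route.
- A reader might infer that the visit schedule cannot be followed. That is so only if Table 2 is read alone, because the other sections allow decision-based timing. It is a wording conflict.
- A reader might infer that the rule biases the comparison in one direction. Ofatumumab holds have the same gap, so the documents do not establish the net direction.

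The reply also bears on the remedy. Running the window to 30 days after the decision could count events up to 42 + 30 = 72 days after last dose. The reported mean duvelisib half-life is only 4.5 to 11.7 hours across the two phase 1 studies, and a decision date involves discretion in an open-label trial. That argues for covering the hold only up to the decision.

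**Conclusion.** The gap is real and narrow. When a hold becomes permanent, AEs and labs that start or worsen after day 30 but before the decision to discontinue are excluded from the treatment-emergent outputs, although they would count had dosing resumed. For duvelisib the uncovered hold time is at most 12 days per subject and is zero when the decision comes by day 30. Subjects who restart have no gap. The most consequential part is the grade-increase rule, which can keep a late Grade 4 or 5 worsening of an on-treatment toxicity out of the maximum-grade and fatal-event tables.

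The number of subjects affected cannot be derived: the documents give no frequency of holds beyond 30 days that end in discontinuation, and a lost event also needs an onset or worsening in those days. The conclusion rests on reading last dose as the last dose taken, and on the ADaM specifications not already dealing with such holds. It does not touch the efficacy analyses.

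**What to change.** For both arms:

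- In SAP 7.3.1, 7.3.2 and 7.3.6, end the window at the later of last dose plus 30 days and the date of the decision to discontinue permanently. Alternatively, keep the 30-day window and add a supplementary summary of AEs, labs and deaths with causes from day 31 through that date.
- Under either option, count a grade increase of an AE with on-treatment onset as treatment-emergent if it occurs in that period, and write this into the ADaM derivation.
- Align AE collection in Protocol Table 2 footnote b, 6.3.4 and 8.2.1, and the ofatumumab equivalent in Table 4 footnote b, so that events during a hold are collected through the decision date.
- Reconcile the ETT and safety-visit anchors across Table 2 and Protocol 4.3, 6.4 and 6.5.1.1.

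No hold or dosing rule needs to change. The cost is wording in both documents, one derived date per subject, and slightly higher AE counts. The decision date should be recorded when the decision is made, to limit discretion over it.

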Study Population:	Approximately 300 subjects with a diagnosis of relapsed and/or refractory CLL or SLL will enroll in the study and be randomized equally to one of two treatment groups: 
 1. Duvelisib 25 mg BID (N=150) 2. Ofatumumab (N=150)
Study Duration:	Study subjects will be followed for survival for up to 6 years from randomization. It is anticipated that the entire study will accrue subjects over approximately 16 months from the randomization of the first subject.
Study Centers:	Enrollment is anticipated at approximately 100 sites, with approximately 25 sites in the US and 75 sites outside the US.
Inclusion Criteria:	Subjects are eligible for inclusion in the study if they meet the following criteria: 
 1. ≥ 18 years of age 2. Diagnosis of active CLL or SLL that meets at least one of the IWCLL 2008 criteria for requiring treatment (Binet Stage \geq B and/or Rai Stage \geq I) 3. Disease that has progressed during or relapsed after at least one previous CLL/SLL therapy 4. Not appropriate for treatment with a purine-based analogue regimen (per National Comprehensive Cancer Network [NCCN] or European Society for Medical Oncology [ESMO] guidelines), including relapse ≤ 36 months from a purine-based chemoimmunotherapy regimen or relapse ≤ 24 months from a purine-based monotherapy regimen 5. A cytogenetics or fluorescence in situ hybridization (FISH) analysis of the leukemic cells within 24 months of randomization is required to document the presence or absence of del(17p). Note: if a sample from within 24 months is not available, it should be evaluated as part of the screening laboratory evaluation to inform stratification 6. Measurable disease with a lymph node or tumor mass > 1.5 cm in at least one dimension as assessed by computed tomography (CT) 7. Eastern Cooperative Oncology Group (ECOG) performance status of 0 to 2 (corresponds to Karnofsky Performance Status [KPS] $\geq 60\%$)

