1.3.2.2 Study IPI-145-02 (Phase 1, Hematologic Malignancies)

Study IPI-145-02 is a Phase 1, open-label, dose-escalation study of duvelisib administered orally twice daily during each 28-day cycles at doses ranging from 8 mg BID to 100 mg BID in adult subjects with advanced hematologic malignancies. Enrollment in all phases of the study is complete, with follow-up ongoing. As of 08 October 2014, 210 subjects received at least one dose of duvelisib including 55 subjects with relapsed/refractory CLL/SLL (8 mg [n=1]; 15 mg [n=2]; 25 mg [n=28]; 75 mg [n=24]). The median time on treatment for all relapsed/refractory subject doses was 5.9 months (range 0.9 to 34.1 months), and 7.6 months (range 0.9 to 34.1 months) for doses \leq 25 mg.²⁰

The maximum tolerated dose (MTD) was determined to be 75 mg BID based upon two dose limiting toxicities (DLTs) experienced by two subjects receiving 100 mg BID (Grade 3 rash and Grade 3 alanine aminotransferase [ALT]/aspartate aminotransferase [AST] elevations). Six expansion cohorts were enrolled at 25 mg BID or 75 mg BID to further define the safety and efficacy of duvelisib in select diseases. The 25 mg dose was selected for phase 3 development based on clinical activity.²¹

Clinical Safety in Relapsed/Refractory CLL/SLL

Frequently occurring (\geq 20% subjects) AEs observed in all relapsed/refractory CLL/SLL subjects (n=55) included neutropenia (53%), rash (combined terms) (46%), diarrhea (44%), cough (38%), fatigue (38%), pneumonia (combined terms) (36%), ALT/AST increased (29%), anemia (29%), pyrexia (27%), nausea (26%), decreased appetite (24%), and thrombocytopenia (22%). Serious adverse events occurring in more than 1 relapsed/refractory CLL/SLL subject included pneumonia (combined terms) (15 [27%]), febrile neutropenia (8 [15%]), diarrhea (3 [5%]), constipation (2 [4%]), hypercalcemia (2 [4%]), pyrexia (2 [4%]), and stomatitis (2 [4%]).²⁰

These events are not unexpected based on the patient population and the mechanism of action of duvelisib. Infection prophylaxis and dose modifications included in the IPI-145-07 protocol are intended to reduce the risk of the frequently occurring events.

Clinical Efficacy in Relapsed/Refractory CLL/SLL

As of 08 October 2014, 52 subjects overall with relapsed/refractory CLL/SLL and 30 subjects who received duvelisib \leq 25 mg BID with relapsed/refractory CLL/SLL had available efficacy data.

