8.2.3.2 Immediate Reporting of Medical Events of Interest

Reports or laboratory results of **AST or ALT > 3x ULN in combination with total bilirubin > 2x ULN are medical events of interest**, and therefore immediately reportable events, even if the events do not meet serious adverse event criteria.

Clinical findings of **Grade 3 or higher rash are medical events of interest**, and therefore immediately reportable events, even if the events do not meet serious adverse event criteria. Pre-existing skin conditions that recur would not meet this definition unless the recurrence is of a greater severity/frequency than previously experienced.

All medical events of interest will be reported to the Sponsor or designee within 24 hours of the Investigator's first knowledge of the event, even if the experience does not appear to be related to study drug. Medical Events of Interest should be communicated on the SAE / Medical Events of Interest (MEOI) report form, as described above for SAEs.

Any occupational exposure or exposure of an individual not enrolled in the study to the investigational medicinal product must be reported to the Sponsor or designee within 24 hours of the Investigator's first knowledge of the event, even if the exposure does not result in an adverse event. Unintentional exposures should be communicated on the SAE/MEOI report form, as described above for SAEs.

8.2.3.3 Reporting of Serious Adverse Events to the Institutional Review Board (IRBs)/ Ethics Committee

Verastem or designee shall notify the Investigator and/or the IRBs/ECs per institutional guidelines of potential serious risks from clinical trials or any other sources, including the following:

- Suspected adverse reaction that is both serious and unexpected.
- Any findings from other studies that suggest a significant risk in humans exposed to the drug.
- Any finding from animal or in vitro testing that suggest a significant risk to humans exposed to the drug, such as mutagenicity, teratogenicity, or carcinogenicity; or report of significant organ toxicity at or near the expected human exposure.

Verastem or designee shall notify Central Ethics Committees (CEC) of new serious, related, and unexpected AE(s) or significant risks to subjects, per country requirements.

The Investigator will notify Local Ethics Committees (LECs) of serious, related and unexpected AE(s) or significant risks to subjects, per local country requirements.

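### No planned adverse-event table gives the by-arm, subject-level incidence of the grouped toxicities that the protocol itself uses, such as rash and pneumonia

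*SAP*

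**What the plan says.** SAP V4.0, section 7.3.1, fixes the level of summary: "TEAEs will be summarized for each treatment arm by MedDRA system organ class (SOC) and preferred term (PT), or PT only". The tables it then lists "will be tabulated by SOC and PT, unless otherwise specified". The list ends with two threshold tables, one all-grade and one for Grade 3 or higher. Each keeps events seen in at least 5% of subjects and at least 2% more often on duvelisib ("higher incidence in subjects receiving duvelisib (All Causalities"). Neither entry specifies a different level. The only aggregation above the preferred term (PT) is the system organ class (SOC), where a subject counts "only once for the number of subjects for the SOC to which this PT belongs". SAP V4.0 defines no grouped terms, standardised queries or events of special interest, and section 7.3 plans no table of medical events of interest.

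The protocol treats some toxicities as groups:
- Section 1.3.2.2, on the phase 1 study, reports "rash (combined terms) (46" and "pneumonia (combined terms) (36" (both percentages of 55 subjects), and serious pneumonia, also as combined terms, in 15 (27%).
- Table 8 in section 4.2.1.1 puts pneumonitis and pneumonia in one category of the duvelisib hold rule.
- Section 8.2.3.2 states that "Grade 3 or higher rash are medical events of interest".

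**The concern.** The protocol uses these concepts to describe phase 1 safety, guide dose holds and trigger expedited reporting, but no planned phase 3 table reports them. A subject with two related PTs appears in two rows, so the rows cannot be summed to give the number of subjects with rash. The SOC count removes that duplication, but it mixes in unrelated events and cannot join terms that sit in different SOCs.

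The threshold tables add a selection effect. A toxicity coded to several PTs must pass both cuts term by term, so minor terms fall out and the remaining rows show less than the whole. Determining duvelisib's safety is a secondary objective, and these two tables are the ones that select events more frequent on duvelisib.

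**Working it through.** **Protocol figures.** 15/55 = 27.3%, stated as 27%, and 20/55 = 36.4%, stated as 36%; both reproduce. The 46% for rash lies between 25/55 = 45.5% and 26/55 = 47.3%, a rounding matter with no bearing here.

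**Inputs.** The planned duvelisib arm is 150 (protocol synopsis). I assume that all are treated and that the 5% applies to this arm. The SAP says only that it is of subjects; with both arms pooled the cut would be 15 of 300.

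**Cut-off.** 0.05 × 150 = 7.5, so a PT needs 8 subjects; with 7 or fewer it is left out.

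**Fixed-count example (assumed rates).** A toxicity in 18/150 (12%) versus 3/150 (2%) passes both cuts as one group. Split evenly over three PTs it is 6 versus 1 per term, 4.0% versus 0.7%. The 3.3-point excess passes, the 4.0% incidence fails, and no row is printed.

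**Chance that no PT reaches 8 subjects.** With true rates p₁,…,p_k and terms treated as independent, this is the product of P(Xᵢ ≤ 7), Xᵢ ~ Binomial(150, pᵢ). P(X ≤ 7) is 0.081 at 8%, 0.317 at 6%, 0.747 at 4%, 0.9166 at 3%, 0.989 at 2% and about 1.000 at 1%.

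For an assumed total of 12%:

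| Split over PTs | Product | No PT reaches 5% |
|---|---|---|
| 8/2/1/1% | 0.081 × 0.989 × 1.000 × 1.000 | 0.08 |
| 6/6% | 0.317² | 0.10 |
| 6/3/2/1% | 0.317 × 0.9166 × 0.989 × 1.000 | 0.29 |
| 4/4/4% | 0.747³ | 0.42 |
| 3/3/3/3% | 0.9166⁴ | 0.71 |

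As one grouped term, 12% reaches 8 subjects with probability 0.998. Six even terms would raise the miss probability to 0.94.

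Other assumed totals, split evenly over two, three and four PTs:
- 8%: 0.56, 0.86 and 0.96 (grouped term reaches the cut with probability 0.92).
- 15%: 0.01, 0.14 and 0.40.

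**Documented rates, same model, four even PTs.**
- 27% (6.75% each): 0.0016.
- 36% (9% each) and 46% (11.5% each): below 0.0001.

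At expected counts, the number of equal terms needed to keep every one at 7 or fewer is the subject count divided by 7, rounded up: 6 terms at 27%, 8 at 36% (54/7) and 10 at 46% (69/7). Even with six equal terms at 27%, sampling variation leaves only a 0.07 chance that none reaches the cut.

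**What the reader would see instead.** With a four-way even split, a 36% pneumonia rate appears as four rows of about 9%, and a 46% rash rate as four rows of about 11.5%. No row shows the whole. If the split is uneven, any term with 7 or fewer subjects leaves the table, and what remains understates the total.

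**The case against.** A reader might infer that rash and pneumonia could disappear from the threshold tables. The documents do not support that: at the only rates they give, the chance is 0.16% or less with four even terms. The 71% needs both an assumed 12% rate and an even four-way split. The documents give no Grade 3 or higher rates for rash or pneumonia, so applying the 5% to 15% range to the Grade 3 threshold table is itself an assumption.

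A reader might also infer that the information is lost, that every table works on single terms, or that phase 1 rates cannot be compared. Each goes too far. SOC counts exist. Section 7.3.1 plans by-arm tables without a cut-off for all TEAEs, maximum grade, Grade 3 or higher, SAEs, holds, reductions, discontinuations and deaths, and by-subject listings from which groups could be rebuilt. Events that phase 1 reported without the combined-terms label, such as diarrhea at 44%, can be compared directly. Neutropenia, thrombocytopenia and ALT/AST are covered by the laboratory shift tables and Grade 3 listings in section 7.3.2.

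Nor is there a contradiction between documents. Protocol section 9.5 asks for tabulations by SOC and PT, and the SAP supplies them; the hold rule and expedited-reporting rule set no analysis requirement. The safety analysis is descriptive, and under protocol section 10.7 the IDMC reviews all available unblinded safety information.

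All of this stands and limits the point. It does not supply a planned by-arm count of subjects with rash or with pneumonia/pneumonitis.

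**Conclusion.** The point holds as a gap in reporting. SAP V4.0 plans no table giving subject-level incidence by arm for toxicities that the protocol handles as groups. For rash and pneumonia the realistic effect is understated displayed incidence. Complete omission from a threshold table is plausible only for toxicities of about 5% to 15%; at an assumed 12% its chance is about 8% to 71% over two to four PTs.

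These figures rest on 150 treated duvelisib subjects, a 5% cut applied to that arm, independent terms, and rates and splits that the documents do not give. Treating the terms as mutually exclusive barely moves the top of the range (about 70%). No test, stopping rule or efficacy conclusion depends on it. Label: cheap improvement.

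**What to change.** Before database lock, add to section 7.3.1 a short list of grouped terms with their constituent PTs: rash, pneumonia/pneumonitis and diarrhea/colitis. Count each subject once per group at maximum grade. Show the groups as extra rows, alongside the PT rows, in the all-grade, Grade 3 or higher, SAE, hold and reduction, discontinuation and death tables and in both threshold tables. State whether the 5% refers to the duvelisib arm, either arm or both pooled. Groups for neutropenia, thrombocytopenia and ALT/AST are optional, since the laboratory tables cover them.

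The cost is agreement on the PT lists, a few more rows and reruns of existing programs. Fixing the lists in advance matters because groups chosen after seeing events by arm would be open to challenge.
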